3.0 PATIENT ELIGIBILITY

3.1 Inclusion Criteria

Subjects must meet all of the inclusion criteria to participate in this study.

- **1.** Ability to understand and the willingness to sign a written informed consent.
- 2. Clinical and phenotypic verification of B cell CLL and measurable disease. Immunophenotyping of the leukemic cells (blood or marrow) must demonstrate a monoclonal (or light chain positive) B cell population with immunophenotype consistent with CLL (e.g., co-expressing CD19 and CD5).
- **3.** Recovered from toxic effects attributed to UC-961 to grade 1 levels, or baseline.
- **4.** Must have measurable disease, including one of the following: absolute lymphocyte count greater than 5000/uL, lymphadenopathy greater than 1.5cm in longest dimension, splenomegaly (palpable at least 1 cm below the costal margin or radiographically enlarged), bone marrow biopsy with residual CLL cells, or resultant bone marrow dysfunction (platelet count < 100k /uL, hemoglobin < 10 g/dL).
- **5.** Women of childbearing potential (not postmenopausal for at least one year or not surgically incapable of bearing children) must agree not to become pregnant for the duration of the study. Both men and women must agree to use a barrier method of contraception for the duration of the study and until 10 weeks after the final dose of UC-961 (expected to be greater than 5 half-lives from pre-clinical data).
- **6.** Subjects must have an ECOG performance status of 0-2.
- **7.** Adequate hematologic function:
 - Platelet count ≥ 50,000/µL unless due to heavily infiltrated bone marrow (> 80% CLL cell infiltrate); AND
 - Hemoglobin ≥ 8.0 g/dL (may be supported by erythropoietin); AND
 - Absolute neutrophil count > 1000 /uL unless due to heavily infiltrated bone marrow (> 80% CLL cell infiltrate).
- 8. Adequate renal function:
 - Serum creatinine <1.5 times upper limit of normal; OR
 - Calculated Creatinine clearance (CrCl) ≥ 40 mL/min (based upon the Cockcroft-Gault Equation [CrCl = (140-age) * actual wt (in kg) * (0.85 if female) / (72 * Cr)].
- **9.** Adequate hepatic function:
 - Total bilirubin ≤ 2.5 times upper limit of normal; AND
 - ALT ≤ 2.5 times upper limit of normal.
- **10.** Adequate coagulation tests:
 - Prothrombin time international normalized ratio (INR) ≤ 2; AND
 - Partial thromboplastin time ≤ 1.66 times upper limit of normal.

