DURATION OF INVESTIGATIONAL AGENT ADMINISTRATION AND STUDY PARTICIPATION

Duration of UC-961 administration is until disease progression, treatment intolerance, or lack of clinical benefit. Patients may remain on the clinical trial protocol until one of the following:

- Clinical or radiographic progressive disease (See Section 12).
- Adverse Events requiring removal from study (See Section 13).
- Refusal of further protocol therapy by patient/parent/guardian
- Non-compliance that in the opinion of the investigator does not allow for ongoing participation.
- Physician determines it is in the patient's best interest to discontinue participation in the clinical trial.
- Completion of all clinical trial procedures.

	Participation in the study and long-term follow-up will continue until one of the following:
	Death.
	Loss to follow-up.
	Withdrawal of consent for any further data submission.
	Progression requiring initiation of subsequent therapy.
	UC-961 is administered by intravenous infusion on day 1, 15, 29, 43, 57, 85, 113, and 141, after which responses will be assessed.
STUDY DRUG ADMINISTRATION	Patients with an objective response (meeting working group criteria for partial response or complete response) will continue at the same dose and schema. Patients with stable disease or progressive disease are eligible to increase the dose of UC-961 for another 6-month course.
CRITERIA TO EVALUATE SAFETY	Safety will be determined by Principal Investigator, and will be assessed according to the NCI Common Terminology Criteria for Adverse Events version 4.03 (NCI CTCAE v4.03) for non-hematologic toxicity and modified iwCLL criteria for hematologic toxicity.
CRITERIA TO EVALUATE EFFICACY	Overall response rate is the percentage of patients meeting criteria for partial response, nodular partial response, or complete response based on iwCLL criteria. Progression free survival is according to iwCLL definition.

Completed UC-961 Phase 1 Clinical Trial (UC-961 q 14 days x 4 doses)

Screen for eligibility for UC-961 Extension Trial

- √ Tolerated UC-961 without dose limiting toxicity and recovered from toxic effects to grade 1 or baseline.
- √ If intervening CLL therapy, maintains measurable disease.

UC-961 q 14 days x 4 doses, then q 28 days x 4 doses (dose based on ongoing phase 1 trial)

Response assessment (labs, imaging, bone marrow biopsy)

Repeat UC-961 course (dose increase if PD or SD)

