1.5 Overview of Proposed Study

UC-961 will be examined for safety and tolerability in patients who enrolled and completed UC-961 infusions on the phase 1 first-in-man clinical trial without dose limiting toxicity at doses at or below the RP2D, and receive retreatment with UC-961 at the established biologically active dose or MTD. The primary endpoint of this phase I trial will be assessment of adverse events during continued treatment. In addition there will be assessment of clinical activity according to iwCLL working group criteria and progression free survival. Additionally, pharmacokinetic parameters will be assessed and blood samples will be collected for correlative analysis.

2.1 Primary Objective:

2.1.1 To determine the safety and tolerability of UC-961 when administered for an extended duration.

2.2 Secondary Objectives:

- 2.2.1 To determine the clinical activity of biweekly doses of UC-961, including overall response rate (2008 iwCLL guidelines) and progression free and overall survival (new clinical endpoint from the initial phase 1 trial).
- 2.2.2 To assess the SD, PR, and MRD- rates

2.3 Exploratory Objectives:

2.3.1 To assess the mechanism of action through immunophenotypic (FACS, ELISA), nanoproteomic ROR1 signaling pathway analysis and pharmacodynamic studies including ROR1⁺ cancer stem cell cycle and self-renewal assays.

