3.2 Exclusion Criteria

Subjects meeting any of the exclusion criteria at baseline will be excluded from study participation.

1. Pregnant or breast-feeding women will not be entered on this study due to risks of fetal and teratogenic adverse events as seen in animal/human studies. IgG may cross the placental barrier and cause fetal B- and T-lymphocyte depletion. Therefore, women of child-bearing age must obtain a pregnancy test, and pregnant or breast feeding females are excluded.

- 2. May have had intervening therapy since completion of initial UC-961 dosing, but excluding the following:
 - Within 7 days of UC-961 restart, or 5 half-lives (if known), whichever is shorter: small molecular tyrosine kinase inhibitor (eg: ibrutinib, idelalisib, AVL-292, IPI-145);
 - b. Within 28 days of UC-961 restart: chemotherapy (e.g., purine analogues, alkylating agents), corticosteroids, radiation therapy, or participation in any other investigational drug treatment (besides UC-961)
 - c. Within 56 days UC-961 restart: previous UC-961 dosing
 - d. Within 56 days of UC-961 restart: monoclonal antibody therapy directed against CLL (eg. rituximab, ofatumumab, obinutuzumab, alemtuzumab).
- 3. Current infection requiring parenteral antibiotics.
- 4. Active infection with HIV, HBV, or HCV.
- 5. Concurrent malignancy or prior malignancy within the previous 3 years (other than completely resected carcinoma in situ, prostate cancer, or localized non-melanoma skin cancer).
- 6. Known central nervous system (CNS) involvement by malignancy.
- 7. Untreated autoimmunity such as autoimmune hemolytic anemia, or immune thrombocytopenia.
- 8. Uncompensated hypothyroidism (defined as TSH greater than 2x upper limit of normal not treated with replacement hormone).
- 9. Presence of more than 55% pro-lymphocytes in peripheral blood. Patients with Richter's transformation are not excluded.
- 10. Insufficient recovery from surgical-related trauma or wound healing.
- 11. Impaired cardiac function including any of the following:
 - Myocardial infarction within 6 months of starting study drug;
 - A past medical history of clinically significant ECG abnormalities.
 - Other clinically significant heart disease (e.g. uncontrolled congestive heart failure, uncontrolled hypertension, history of labile hypertension, or history of poor compliance with an antihypertensive regimen)

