4.2 Dose Limiting Toxicity

Dose-Limiting Toxicity (DLT) is defined as any of the following adverse events that are considered by the investigator to be possibly, probably, or definitely related to the study agent UC-961 within the 28 days of the start investigational treatment:

- CTCAE Grade 3 or higher non-hematologic toxicity, except for: Grade 3 infections lasting < 7 days that have resolved, or one occurrence of Grade 3 infusion reaction; or
- Grade 4 or higher hematologic toxicity (by modified iwCLL criteria); or
- Any AE requiring a dose delay of greater than 28 days;

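### The schema bars patients who had a dose-limiting toxicity in phase 1, but the numbered eligibility criteria do not

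*Combined protocol and SAP*

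**What the plan says.** Two places describe who may enter with respect to earlier UC-961 treatment.

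- The synopsis schema starts from a completed phase 1 course of four doses at 14-day intervals. Its eligibility-screening step then requires: "Tolerated UC-961 without dose limiting toxicity and recovered from toxic effects to grade 1 or baseline".
- Section 1.5 describes the study population as patients who "completed UC-961 infusions on the phase 1 first-in-man clinical trial without dose limiting toxicity".

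The numbered lists say less. Section 3.1 opens with "Subjects must meet all of the inclusion criteria to participate in this study" and Section 3.2 with "Subjects meeting any of the exclusion criteria at baseline will be excluded from study participation". Their only conditions on earlier UC-961 are these:

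- Inclusion item 3: "Recovered from toxic effects attributed to UC-961 to grade 1 levels, or baseline".
- Exclusion 2c: "Within 56 days UC-961 restart: previous UC-961 dosing".

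The lead-in to exclusion 2 reads "May have had intervening therapy since completion of initial UC-961 dosing, but excluding the following". It takes completed initial dosing as given and does not require it. The synopsis repeats item 3 and the 56-day washout. Its statement on patient numbers says, without qualification, that patients who enrolled in phase 1 may enroll here.

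**The concern.** Sites normally screen from the numbered list. A site that does so here can reach an entry decision that the schema rejects.

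The patient in question is one whose phase 1 DLT has resolved. That patient would be re-treated at the highest safe phase 1 dose, which is 8 mg/kg at the time of writing (Sections 1.4 and 4.1). This may exceed the dose the patient had before, because Section 1.1 provides for patients first treated below the recommended phase 2 dose. In course 2 the dose would rise only for stable or progressive disease, and only if phase 1 had by then established a higher safe dose.

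Section 10 names the DLT rate as the primary endpoint, so whether such patients may enter also affects which population that rate describes.

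**Working it through.** No arithmetic is needed beyond counting. The check has four steps.

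**1. Compare the texts, condition by condition.**

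| Condition on earlier UC-961 | Schema | Section 1.5 | Section 3 lists | Synopsis lists |
|---|---|---|---|---|
| Phase 1 dosing completed | yes | yes | no | no |
| No phase 1 DLT | yes | yes | no | no |
| Toxicity recovered | yes | not stated | yes (item 3) | yes (item 3) |
| 56-day washout | not stated | not stated | yes (exclusion 2c) | yes (exclusion 2c) |

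Section 3 has 10 inclusion + 12 exclusion = 22 numbered items, and the synopsis also has 10 + 12 = 22. In each list, 0 of 22 require completion or the absence of a DLT. Section 3 is present in full, so missing text does not explain the gap. The schema's other two screening conditions, recovery and measurable disease, did reach the list as items 3 and 4. This suggests that the remaining conditions were left out in drafting.

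**2. Apply both sets of rules to one patient.** Suppose a patient had a related Grade 3 non-hematologic event in phase 1 that counted as a DLT there. It has resolved to Grade 1, more than 56 days have passed since the last dose, and every other item is met. The numbered lists raise no bar. The schema says no, and the patient falls outside the Section 1.5 population.

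**3. Look for a later rule that would catch this patient.**

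- Section 4.2 counts events "related to the study agent UC-961 within the 28 days of the start investigational treatment". Read as a rule for this study, it does not reach back to phase 1.
- Section 4.5 withholds a dose only for toxicity that is still ongoing.
- Section 4.6 stops treatment for a DLT as Section 4.2 defines it.

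None of these screens for an earlier DLT that has resolved. The schedule of events lists an Eligibility Checklist, but its content is not reproduced.

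**4. Gauge how many patients could be affected.** The phase 1 table to 1 April 2016 covers events judged probably, possibly or unlikely due to UC-961. It has 31 rows.

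- Grade 1: the first 12 rows give 6 + 4 + 3 + 4 + 3 + 3 + 3 + 1 + 2 + 2 + 2 + 2 = 35. The amylase and confusion rows give 0, and the last 17 rows give 1 each, so 35 + 17 = 52.
- Grade 2: thrombocytopenia, neutropenia, lipase, amylase and confusion give 1 each, so 5.
- Above Grade 2: none.

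The counts sum to 52 + 5 = 57. The table is not a complete tally, because the accompanying text mentions a Grade 2 urinary tract infection that has no row. That event is also below Grade 3.

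**The case against.** The strongest reply is that the numbered lists are silent rather than contradictory. The opening sentence of Section 3.1 makes the inclusion items necessary, and that of Section 3.2 makes each exclusion disqualifying. Neither says that the lists are exhaustive. They do not even require phase 1 enrollment, which comes from the title and the synopsis, so they already depend on text elsewhere. The schema condition stands under an eligibility-screening step, and a site that read the whole protocol would apply it. Section 1.5 is an overview and is not worded as an entry rule.

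This stands as far as it goes. A reader might infer that Section 3 authorizes entry after a DLT, or that its lists alone decide entry. The documents do not say so. What remains is that one screening step states a condition which the list built for screening omits, while the synopsis calls phase 1 enrollees eligible without qualification. The site is left to notice the mismatch and settle it.

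Two further objections have force. The schema gives no reason for its condition, so calling it a safety bar is a plausible inference and not a stated rationale. Requiring completion would also exclude someone who left phase 1 early for a reason other than a DLT, whom the numbered lists and the synopsis sentence do not exclude.

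**Conclusion.** The inconsistency is real: the schema and the numbered criteria give different answers for a patient whose phase 1 DLT has resolved. It should be corrected, but its practical weight is modest.

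A reader might infer that such patients have been or will be re-treated, or that they lack protection once enrolled. The documents support neither. No affected patient is shown, and the number to date may be zero. Sections 4.6 and 4.9 still provide treatment discontinuation for a DLT, dose modification and enrollment holds for new toxicity. The gap is at entry. It looks forward because phase 1 was still under way, with 16 and 20 mg/kg listed as potential levels.

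The conclusion assumes that the Eligibility Checklist does not already carry the condition, which cannot be seen. The phase 1 DLT definition and the phase 1 rules after a DLT are not visible either. If phase 1 stopped dosing after a DLT, the numbered lists would still not bar the patient, because they do not require completion.

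**What to change.** Add one item to Section 3.1 and to the synopsis inclusion list, for example: *Received the full phase 1 course of UC-961 and had no dose-limiting toxicity on that trial, as defined in the phase 1 protocol.* Keep item 3 as a separate condition. In the synopsis statement on patient numbers, make the eligibility of phase 1 enrollees subject to the eligibility criteria. If the Eligibility Checklist lacks the condition, add it there too.

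The no-DLT condition is the essential part. The schema and Section 1.5 both call for completion as well, but the sponsor should confirm that this is meant to exclude patients who stopped phase 1 early for other reasons. If it is not, the completion wording should be relaxed in all four places (schema, Section 1.5, Section 3.1 and synopsis list).

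The cost is one sentence in two lists and a short qualifier. No analysis changes. The no-DLT condition is already in the schema, so adding it to the lists sets no new policy.

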3.2 Exclusion Criteria

Subjects meeting any of the exclusion criteria at baseline will be excluded from study participation.

1. Pregnant or breast-feeding women will not be entered on this study due to risks of fetal and teratogenic adverse events as seen in animal/human studies. IgG may cross the placental barrier and cause fetal B- and T-lymphocyte depletion. Therefore, women of child-bearing age must obtain a pregnancy test, and pregnant or breast feeding females are excluded.

- 2. May have had intervening therapy since completion of initial UC-961 dosing, but excluding the following:
 - Within 7 days of UC-961 restart, or 5 half-lives (if known), whichever is shorter: small molecular tyrosine kinase inhibitor (eg: ibrutinib, idelalisib, AVL-292, IPI-145);
 - b. Within 28 days of UC-961 restart: chemotherapy (e.g., purine analogues, alkylating agents), corticosteroids, radiation therapy, or participation in any other investigational drug treatment (besides UC-961)
 - c. Within 56 days UC-961 restart: previous UC-961 dosing
 - d. Within 56 days of UC-961 restart: monoclonal antibody therapy directed against CLL (eg. rituximab, ofatumumab, obinutuzumab, alemtuzumab).
- 3. Current infection requiring parenteral antibiotics.
- 4. Active infection with HIV, HBV, or HCV.
- 5. Concurrent malignancy or prior malignancy within the previous 3 years (other than completely resected carcinoma in situ, prostate cancer, or localized non-melanoma skin cancer).
- 6. Known central nervous system (CNS) involvement by malignancy.
- 7. Untreated autoimmunity such as autoimmune hemolytic anemia, or immune thrombocytopenia.
- 8. Uncompensated hypothyroidism (defined as TSH greater than 2x upper limit of normal not treated with replacement hormone).
- 9. Presence of more than 55% pro-lymphocytes in peripheral blood. Patients with Richter's transformation are not excluded.
- 10. Insufficient recovery from surgical-related trauma or wound healing.
- 11. Impaired cardiac function including any of the following:
 - Myocardial infarction within 6 months of starting study drug;
 - A past medical history of clinically significant ECG abnormalities.
 - Other clinically significant heart disease (e.g. uncontrolled congestive heart failure, uncontrolled hypertension, history of labile hypertension, or history of poor compliance with an antihypertensive regimen)
- 12. Patients who in the opinion of the investigator may be unable to comply with the safety monitoring requirements of the study.

4.0 INVESTIGATIONAL TREATMENT PLAN

4.1 Dose Assignment

The dose of UC-961 is currently undergoing evaluation in a phase 1 study.

During the extension treatments, patients will be assigned to receive the highest safe dose from an ongoing phase 1 study, or the established maximum tolerated dose/ recommended phase 2 dose (which may increase as the phase 1 trial accrues additional patients). Patients will receive the same dose of UC-961 for 1 course, which consists of 8 doses (every 14 days for 4 doses, then every 28 days for 4 doses). As of April 2016, the highest safe dose is 8 mg/kg.

Following 1 course, patients will be assessed for response, and then are eligible to receive a second course. Patients with a complete response or partial response will continue at the same

dose. Patients with stable disease or progressive disease will receive a higher dose of UC-961, if a higher safe dose has been established in the concurrent CLL Phase 1 trial by that time.

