	6 OBLIGATIONS OF INVESTIGATORS	
12.0	REFERENCES	40
13.0	APPENDICES	41
APP	PENDIX A. PERFORMANCE STATUS	41

	T
INVESTIGATIONAL AGENT	UC-961
TITLE	A Phase 1B Extension Study to Determine the Safety, Pharmacokinetics and Pharmacodynamics of UC-961 (Cirmtuzumab) at the recommended phase 2 dose for patients with Chronic Lymphocytic Leukemia Previously Treated with Cirmtuzumab (UC-961).
PROTOCOL NUMBER	
PHASE OF DEVELOPMENT	Phase IB
STUDY OBJECTIVES	 To determine the safety and tolerability of UC-961 when administered for an extended duration. Secondary Objectives: To determine the clinical activity of biweekly doses of UC-961, including overall response rate (2008 iwCLL guidelines) and progression free and overall survival (new clinical endpoint from the initial phase 1 trial). To assess the SD, PR, and MRD- rates Exploratory Objectives: To assess the mechanism of action through immunophenotypic (FACS, ELISA), nanoproteomic ROR1 signaling pathway analysis
STUDY ENDPOINTS	and pharmacodynamic studies including ROR1* cancer stem cell cycle and self-renewal assays. Primary Endpoint Safety and tolerability with extended dosing of UC-961 based on ongoing evaluation of AEs during treatment and 3 month follow up Secondary Endpoints 1. Overall response rate by IWCLL criteria following 6 months of biweekly dosing of UC-961 (Hallek et al., 2008) 2. Progression free and overall survival (progression determined by IWCLL working group criteria) 3. SD, PR, and MRD- rates, as well as individual components of response (reduction in leukemia count, reduction in adenopathy and splenomegaly, and improvement in BM function), as determined by IWCLL working group criteria. Exploratory Endpoints 1. ROR1 receptor density on circulating bulk tumor cells and stem cells 2. Circulating UC-961 levels in peripheral blood 3. Level of circulating antibodies against UC-961 4. Assay of ROR1 signaling via nanoproteomics (CB1000) 5. Assay of cytokine signaling and other CLL signaling pathways via qPCR array. 6. Assay of associated proteins including phosphorylated AKT versus total AKT ratio by western blot 7. Assay of ROR1* cancer stem cell inhibition by stromal co-culture FUCCI2BL cell cycle, survival and self-renewal analysis
STUDY DESIGN	This is an open-label extension study to determine the safety and efficacy.
31001 DESIGN	The is an open laber extension study to determine the safety and emeacy.

NUMBER OF PATIENTS

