The study proposed herein will allow patients who wish to continue UC-961 therapy to receive continued UC-961 at the biologically active dose or recommended phase 2 dose (RP2D). It will also allow patients that were initially treated at doses below the RP2D to increase their dose of UC-961. It will also allow for improved data regarding long-term safety and safety with prolonged dosing of UC-961 at the R2PD.

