1.4 Rationale for Dose Selection

Each extension course consists of 8 infusions. A patient may repeat the course, and therefore receive a total of 16 infusions on the extension study. Each individual patient will receive the same

dosage of UC-961 for each of the 8 infusions of each course. The dosage of UC-961 may be increased for the 2nd set of 8 infusions (if a higher dose has been shown to be safe on the phase 1 trial AND there is Progressive Disease or Stable Disease after the first course of extension.

The dose administered on this extension study will be the highest safe dose, or once established, the biologically active dose or the recommended phase 2 dose from the phase 1 trial. To date, the 8 mg/kg dose level has been completed and determined to be safe. Therefore, patients on this extension study will begin at the 8 mg/kg dose level. Should subsequent dose levels be determined to be safe in the Phase 1 trial, the dose utilized in this trial may increase for subsequent patients.

Planned dose levels (starting dose is the highest safe dose administered to a patient in the phase 1 trial):

Potential	Dose		
Dose Level			
-1	4 mg/kg		
1 (start)	8 mg/kg		
2	16 mg/kg (or max 2000 mg dose)		
3	20 mg/kg (or max 2000 mg dose)		

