10.0 STATISTICAL CONSIDERATIONS

The primary aim of the study is to determine the safety of UC-961 therapy given at the currently used, biologically active dose, or RP2D for an extended duration.

Safety will be assessed through summaries of adverse events, clinical laboratory abnormalities, and changes in physical exam and vital signs. All subjects who receive a single dose of study medication will be considered evaluable for safety.

Adverse events will be listed, documenting the course, outcome, severity, and relationship to the study treatment. Incidence rates of AEs and the proportion of subjects prematurely withdrawn from the study due to AEs will be shown.

The primary endpoint of this study is the rate of dose-limiting toxicity (DLT).

SECONDARY ANALYSIS

Secondary Endpoints are overall response rate by IWCLL criteria following 6 months of biweekly dosing of UC-961 (Hallek *et al.*, 2008); Progression free and overall survival (progression determined by IWCLL working group criteria); and SD, PR, and MRD-rates, as well as individual components of response (reduction in leukemia count, reduction in adenopathy and splenomegaly, and improvement in BM function), as determined by IWCLL working group criteria.

These secondary endpoints will be summarized by dose cohort, clinical characteristics and overall using percentages, means and median survival estimates as appropriate. Data will also be presented graphically with Kaplan Meier plots, box plots, and bar charts. All statistics will be presented with 95% confidence intervals. The analysis will be descriptive; thus no correction for multiple analyses will be made and no formal tests of hypothesis will be done.

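### The sections that set the extension dose name different targets without a visible order of precedence, and the planned safety summaries are not split by dose, so the primary result is not tied to any one dose.

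*Combined protocol and SAP*

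**What the plan says.** The study title in the synopsis describes treatment "at the recommended phase 2 dose for patients with Chronic Lymphocytic Leukemia". Section 1.1 permits the biologically active dose or the RP2D, and gives as one purpose better data on "safety with prolonged dosing of UC-961 at the R2PD" (the last term is evidently RP2D).

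Section 1.4 sets the dose as "the highest safe dose, or once established, the biologically active dose or the recommended phase 2 dose from the phase 1 trial". Section 1.5 says patients will "receive retreatment with UC-961 at the established biologically active dose or MTD". Section 4.1, headed Dose Assignment, has them "assigned to receive the highest safe dose from an ongoing phase 1 study, or the established maximum tolerated dose/ recommended phase 2 dose", and adds that this may rise as phase 1 accrues. Section 10 describes the primary aim as safety of therapy "given at the currently used, biologically active dose, or RP2D for an extended duration".

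Sections 1.4 and 4.1 agree that 8 mg/kg is the dose at the time of writing. Section 1.4 lists 16 and 20 mg/kg as possible higher levels and lets later patients start higher. For Course 2, Section 4.1 keeps responders at their dose, while patients with stable or progressive disease "will receive a higher dose of UC-961, if a higher safe dose has been established in the concurrent CLL Phase 1 trial".

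In Section 10 anyone who received a single dose is evaluable for safety. Summaries by dose cohort are specified for the secondary endpoints only.

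**The concern.** The dose rule settles two things: what a patient receives, and which dose the primary safety result describes. Here the target changes from section to section among four terms: highest safe dose, biologically active dose, MTD and RP2D. Phase 1 was still escalating when this was written, and the adverse event table for that trial shows nothing above grade 2. A biologically active dose below the MTD or the RP2D is therefore a foreseeable outcome, and the sections would then no longer permit the same doses.

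The dose can also change between patients and, at Course 2, within a patient. If adverse events and DLTs are then pooled over everyone treated, the resulting rate belongs to a mixture of doses. It could not support the purpose given in the title and Section 1.1, which is safety with prolonged dosing at the RP2D.

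**Working it through.** The plan gives no sample-size, power or precision figure on this point, so there is none to reproduce.

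**1. Targets side by side.**

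| Place | Target once phase 1 has established it |
|---|---|
| Title | RP2D |
| 1.1 | biologically active dose or RP2D |
| 1.4 | biologically active dose or RP2D (highest safe dose until then) |
| 1.5 | biologically active dose or MTD |
| 4.1 | MTD/RP2D (or highest safe dose) |
| 10 | biologically active dose or RP2D (or the dose in current use) |

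Section 4.1 is the only numbered section here that omits the biologically active dose. Section 1.5 is the only one that does not offer the RP2D as a target.

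**2. How often the permitted doses differ.** Let B, R and M be the biologically active dose, RP2D and MTD, each on the listed levels 8, 16 and 20 mg/kg. Two assumptions are mine: B ≤ R ≤ M, and M also stands for the highest safe dose. The interim options in 1.4 and 10 are set aside. The permitted sets are then {B, R} for 1.1, 1.4 and 10; {B, M} for 1.5; and {R, M} for 4.1.

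- All three equal: 3 orderings. Every section permits the same single dose.
- B = R < M: 3 orderings. Sections 1.1, 1.4 and 10 permit R only; 1.5 and 4.1 permit R or M. R is common.
- B < R = M: 3 orderings. Section 4.1 permits R only; the others permit B or R. R is common.
- B < R < M (8, 16, 20): 1 ordering. Sections 1.1, 1.4 and 10 permit {8, 16}, 1.5 permits {8, 20}, and 4.1 permits {16, 20}. No dose is common to all.

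In total 3 + 3 + 3 + 1 = 10 orderings. The permitted sets differ in 7 and share no dose in 1. These are counts of possibilities, not probabilities.

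**3. Course 2.** For stable or progressive disease, the synopsis (study drug administration) makes patients eligible for an increase, Section 1.4 allows one, and Section 4.1 states it as what will happen. All concern the same patients, and none says how the increase relates to the RP2D. Because responders keep their dose, a responder who began at 8 mg/kg stays there whatever phase 1 later declares. The rules can therefore leave some patients below the RP2D and take others above it.

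**4. Effect on the safety result.** With no events among n patients, the exact two-sided 95% upper limit is 1 − 0.025^(1/n).

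- n = 33 (anticipated enrolment): 10.6%
- n = 75 (maximum eligible): 4.8%
- n = 17 or 16 (about half of 33): 19.5% or 20.6%
- n = 11 (33/3): 28.5%

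The documents do not say what share will be treated at the RP2D, so the last two lines rest on assumed splits.

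**The case against.** The strongest reply is that the operative section is already identified. Section 5.2.7 sends the reader to 4.1 for the dose, and 4.1 also holds the Course 2 rule. Sections 1.1, 1.4 and 1.5 are background, rationale and overview. This largely answers any suggestion that two investigators would dose the same Course 1 patient from different sections. Section 5.4.7 does not repeat the reference for Course 2.

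The targets are also joined by alternatives, so the sections permit doses rather than each fixing one. Once an RP2D is declared, giving it satisfies every place listed except possibly 1.5. That stands too: in the enumeration it fails only in the ordering where all three targets separate.

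A reader might infer a definite gap: 8 mg/kg under 1.4 and 10 against 20 mg/kg under 4.1, which is 20/8 = 2.5-fold. The documents do not support that. It takes one branch of each alternative and leaves the RP2D unstated. An RP2D of 8 mg/kg would let 4.1 reach the lower dose, and one of 20 mg/kg would let 1.4 and 10 reach the higher. It also treats the highest safe dose in 4.1 as lasting, although it reads as an interim rule.

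A reader might also infer that the plan will label pooled results as safety at the RP2D. No planned analysis does so: objective 2.1.1 and endpoint 2.4.1 name no dose, and Section 10 names three alternatives. Only the title and one sentence of 1.1 carry that claim.

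Finally, Section 1.3, to which 1.1 refers for phase 1 details, is not fully visible in the available text. A ranking of the targets could sit there or in the phase 1 protocol.

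None of this gives the biologically active dose a place in 4.1, settles whether the Course 2 increase is optional, or adds dose to the safety tables.

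**Conclusion.** The concern holds as an inconsistency to be reconciled and a gap in the safety analysis. It does not show that patients are being assigned conflicting doses. At 8 mg/kg the sections agree, so the conflict over targets is latent and depends on phase 1 separating the biologically active dose, RP2D and MTD. Under the assumed ordering, the permitted sets differ in 7 of 10 cases and exclude any common dose in 1.

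Two parts do not wait on that outcome. The wording of the Course 2 increase already conflicts on whether it is optional. Section 10 already specifies no adverse event or DLT summary by dose, although the plan allows the dose to change between and within patients. As specified, the primary result would describe a mixture of doses. A statement confined to the RP2D would be less precise than the pooled one, by an amount that depends on a share the documents do not give: the upper limit goes from 10.6% to 28.5% if that share is one third of 33 and no events occur.

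**What to change.** - **Section 4.1:** reconcile the passages into one dose-assignment rule, with an order of precedence for when the highest safe dose, biologically active dose, MTD and RP2D differ. Use one wording for the Course 2 increase and state how it relates to the RP2D. Which dose applies, and whether the increase is optional, are the sponsor's decisions.
- **Synopsis and Sections 1.1, 1.4, 1.5, 5.4.7 and 10:** refer to that rule instead of restating it, and bring the title into line.
- **Section 10:** summarise adverse events and DLTs by dose actually received, and by course where the dose changes. Define dose cohort for patients whose dose changes. Keep the pooled summary, but limit any safety statement at the RP2D to exposure at that dose. Read literally, the DLT window in 4.2 closes 28 days after treatment starts, before any Course 2 increase, so the adverse event tables by course must carry that information.

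The cost is amendment wording and additional tables, with no extra patients, visits or procedures. The drawback is that a statement at the RP2D may rest on fewer patients and wider intervals.
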